7.6.5.8 Liver Function Abnormalities

When liver function abnormalities meet any of the following criteria the investigator must report these abnormalities to the sponsor within 24 hours:

- AST or ALT > 3 \times upper limit of normal (ULN) and total bilirubin (TBL) > 2 \times ULN
- AST or ALT > 3 × ULN and prothrombin time international normalized ratio (PT-INR) > 1.5

In addition, liver function abnormalities meeting any of the following criteria need to be managed according to Appendix 5:

- AST or $ALT > 5 \times ULN$
- AST or ALT $> 3 \times$ ULN with signs and symptoms compatible with hepatitis or hypersensitivity

7.6.5.9 Special Situations - Abuse, Misuse, Overdose, and Medication Error

Abuse, misuse, overdose, or medication error of the study drug (as defined below) must be reported to the CRO or sponsor (the sponsor's medical monitor) via fax by the investigator using a Special Situations Report Form as soon as possible. If the special situation that occurred is an SAE, the investigator will complete the SAE Form as well.

- Abuse persistent or sporadic, intentional excessive use of an investigational product(s), which is accompanied by harmful physical or psychological effects
- Misuse intentional and inappropriate use of an investigational product(s) other than as directed or indicated at any dose
- Overdose intentional or unintentional intake of a dose of investigational product(s) higher than the assigned dose in the protocol
- Medication Error any unintended error in the prescribing, dispensing or administration of an investigational product(s); cases of patients missing doses of investigational product(s) are not considered reportable as medication errors

7.6.5.10 Pregnancy

If a female patient becomes pregnant during the study, the investigator (or subinvestigator) must instruct her to discontinue all study drugs and inform the sponsor immediately. In addition, the investigator (or subinvestigator) must attempt to collect pregnancy information on any female partners of male study patients who become pregnant while the patient is enrolled in the study. Pregnancy information must be reported to the CRO or sponsor as described below.

All pregnancies that occur after the first dose of the study drug through the follow-up period must be reported to the sponsor or CRO within 24 hours of the investigator (or subinvestigator) becoming aware of the pregnancy and the Pregnancy Form will be faxed to the sponsor or CRO by the investigator. Pregnancy complications and elective terminations for medical reasons must also be reported as an AE or SAE as appropriate. Spontaneous abortions must be reported as an SAE. The outcome of the pregnancy should be followed and must also be reported using the Pregnancy Form, which must be faxed to the sponsor. All pregnancies that are confirmed after the follow-up visit but within 3 months of last study drug dose should be reported to the sponsor and followed to completion by the study site. At the end of the pregnancy (ie, birth, miscarriage, abortion), the outcome should be reported to the CRO or sponsor.

7.7 Other Assessments

7.7.1 Serum Influenza Antibody Titer Test

Blood samples will be collected predose at Visit 1 (Day 1) and Visit 7 (Day 22). Specimens will be handled according to Section 7.6.4.5.

The clinical laboratory will measure serum antibody titers for the influenza A and B viruses.

7.7.2 Polymorphic and Treatment-emergent Amino Acid Substitutions

As a part of the virology testing, PA gene sequencing of virus will be performed to evaluate the incidence and characteristics of polymorphic and treatment-emergent amino acid substitutions in patients with evaluable virus. This sequencing will be performed using specimens obtained from all patients in the S-033188 treatment group and 100 patients in the placebo group. The virology testing facility (see Section 10.1) will perform the gene sequencing according to procedures or a protocol specified in a separate document. Access to the gene sequencing data will be limited. Specific details of who will have access to each endpoint will be specified in a separate document.

7.7.3 Drug Susceptibility Testing for Test Substances

As a part of the virology test, the ViroSpot[™] assay and the NA-star[®] assay will be performed to evaluate the drug susceptibility for S-033188 and oseltamivir acid using evaluable virus at baseline sample in patients. The virology testing facility (see Section 10.1) will perform the drug susceptibility testing according to procedures or a protocol specified in a separate document.

7.7.4 Health Economic Outcomes

7.7.5 Work Productivity Questionnaire

The WP questionnaire will be completed at Day 22, or at the earliest clinic visit following alleviation of symptoms. These assessments are included in Appendix 3. The work productivity questionnaire consists of 4 questions regarding employment, number hours worked, productivity while at work, and requirement for personal assistance.

The work productivity questionnaire will be completed on paper.

7.8 Withdrawal of Patients from the Study or Study Treatment

The investigator will make every reasonable attempt to complete the study for each enrolled patient. A patient may withdraw for any reason. The investigator will advise the sponsor about the withdrawal of any patient by the IWRS.

The investigator will withdraw a patient from the study or the study drug treatment for any of the following reasons:

- A serious or intolerable AE occurs and the investigator considers that the patient should be withdrawn because of the AE
- The patient requests to be withdrawn from the study
- The patient is lost to follow-up
- The investigator determines that the patient should be withdrawn because of other reasons
- The investigator determines that the patient should be withdrawn based on the management and discontinuation criteria for abnormal liver function tests

In the event of a patient's withdrawal, the investigator will promptly notify the sponsor and will make every effort to complete the end-of-study (or ET) assessments. All patients withdrawn due to AEs will be followed until resolution of any AEs, until the unresolved AEs are judged by the investigator to have stabilized, or the patient is lost to follow-up. The date of completion (if completed the follow-up period), date of discontinuation (if discontinued before Day 22), period of discontinuation, and reason for discontinuation will be entered in the eCRF.

7.8.1 Clinical Progression or Lack of Response

In cases where on clinical review, patients appear to be deteriorating clinically or have not responded to the study drug, the investigator should consider the possibility of secondary infections, decompensation of underlying conditions, or progression of influenza. Patients should be assessed, and investigations should be performed as clinically indicated.

In the event an investigator considers that the influenza has not responded and wishes to treat with open-label, commercially-available influenza antivirals (not provided by the sponsor), the patient should stop all blinded study drugs. Since unblinding of the study drugs would not alter the management of the patients, unblinding in this situation is discouraged, and the patients should remain in the study for follow-up as described in Section 7.8. Such cases should be discussed urgently with the sponsor or sponsor's designated Medical Monitors.

7.9 Appropriateness of Measurements

7.9.1 Primary Efficacy Endpoint

The time to improvement of symptoms is defined as the time to improvement of 7 influenza symptoms (cough, sore throat, headache, nasal congestion, feverishness or chills, muscle or joint pain, and fatigue). The time to alleviation of symptoms has been commonly used as a measure of the efficacy of anti-influenza virus drugs, thereby enabling a comparison with the results from clinical studies of currently available medications. Since some "high risk" individuals may have underlying chronic diseases that share some symptoms with those of influenza (ie, cough in a patient with chronic lung disease), a modification of time to alleviation has been included in this protocol to permit improvement of a symptom that may have been present before the onset of influenza but worsened by influenza, or maintenance of a preexisting symptom that has not been worsened by the onset of acute influenza. This is a novel and untested endpoint but is considered by the sponsor to be a reasonable approach to avoid confounding of results due to persistent preexisting symptoms that cannot be completely alleviated.

7.9.2 Secondary Efficacy Endpoints

Available nonclinical data suggest that a single oral dose of S-033188 can provide rapid relief of influenza symptoms. In addition, influenza symptoms were relieved significantly earlier in patients who received a 40-mg single oral dose of S-033188 compared to placebo in the Phase 2 proof-of-concept and dose-finding study (Study 1518T0821).

The time to cessation of viral shedding by virus titer and by reverse transcription polymerase chain reaction (RT-PCR) will provide data to indicate when both culturable viable virus and viral elements have become undetectable by viral titer and PCR, respectively. This permits an evaluation of 'viral shedding' that is analogous to infectivity, where an index case (the patient) is producing virus in nasal secretions and can infect close contacts.

In addition, the efficacy of S-033188 can be examined in detail by assessing the changes over time in the scores of symptoms and the time to resolution of fever.

Examining the change from baseline in influenza virus titer will enable the assessment of the relationship between antiviral activity and clinical symptoms.

An assessment of the intra-household infection rate will provide useful information on the transmissibility of influenza infection after treatment with S-033188.

7.9.3 Other Endpoints

The benefits of S-033188 in improving QOL can be examined by assessing the time to return to preinfluenza health status and the change in the score of the QOL questionnaire CPI

An understanding of potential amino-acid substitutions in S-033188-exposed patients will be gained by exploring polymorphic and treatment-emergent amino acid substitutions in

the PA gene in S-033188-exposed patients at baseline and at the last evaluable time point, with sequencing of approximately 100 placebo-exposed patients performed as a control.

7.9.4 Safety Endpoints

Monitoring patients for AEs and treatment-related AEs will provide important information to examine the safety and efficacy of S-033188.

7.9.5 Plasma Drug Concentrations

Assessing the PK of S-033447 in patients will provide important information for the future clinical use of S-033188.

8. STUDY ACTIVITIES

The overall schedule of events for the study is presented in Appendix 1.

8.1 Poststudy Access to the Study Drug

There will be no availability of study drug once the patient has completed the study.

9. PLANNED STATISTICAL METHODS

9.1 General Considerations

The statistical analysis and PK analysis will be performed by the sponsor or a designee. The detailed statistical analysis methods will be specified in a statistical analysis plan (SAP) and PK analysis plan according to this section of the study protocol. If analyses deviated from those outlined in the protocol, the reason for deviation from the protocol will be described in the SAP and PK analysis plan. The SAP and PK analysis plan will be finalized before scheduled unblinding.

Unless otherwise noted, continuous variables will be summarized by using the number of nonmissing observations, arithmetic mean, standard deviation, median, minimum, and maximum values as descriptive statistics; categorical variables will be summarized by using the frequency count and the percentage of patients in each category as descriptive statistics.

All statistical tests will be performed at the 0.05 significance level using 2-sided tests, except where otherwise noted. The primary endpoint will first be compared between the S-033188 and placebo groups for patients (primary analysis). Together with the primary efficacy analysis, a comparison between the S-033188 group and the oseltamivir group (secondary analysis) will be conducted in a hierarchical manner so as to maintain control of overall type I error. For Japan, control of overall type I error is not required for the secondary efficacy analysis of the primary endpoint. All patient study data will be presented in listings. In general, all tables will be presented by treatment group. Individual patient data will be presented by treatment and by patient. All analyses and tabulations will be performed by using both SAS[®] Version 9.2 or higher and WinNonlin[®] Version 6.2.1 or higher.

9.2 Determination of Sample Size

The required sample size of the intention-to-treat infected (ITTI) population is 1185 patients (395 patients for each treatment group). It is assumed that the RT-PCR-positive rate will be 55% of the randomized population. Therefore, 2157 patients (719 patients for each treatment group) will be randomized to ensure an adequate number of patents in the ITTI population. The number of randomized patients may change based on the percentage of patients who are RT-PCR positive during the study.

Rationale for the Target Sample Size

The primary analysis of the time to improvement of influenza symptoms is to compare between the S-033188 group and placebo group.

The median of the time to alleviation of symptoms in the placebo-controlled clinical trial of oseltamivir for high risk patients was estimated to be 161.0 hours (95% CI: 117.3, 215.5) in the placebo group [6]. Based on this result and the fact that the proposed study

will use a modified primary endpoint, it was assumed that the median time to improvement of influenza symptoms in the placebo group will be 150 hours.

In the Japanese Phase 2 clinical trial in otherwise healthy patients, the median of the time to alleviation of symptoms was 49.5 hours (95% CI: 44.5, 64.4) in the 40-mg group versus 77. 7 hours (95% CI: 67. 6, 88.7) in the placebo group. Assuming the ratio of 0.64 (= 49.5/77.7) for the median time to alleviation of symptoms in the S-033188 group versus the placebo group is not different between otherwise healthy patients and high risk patients, it can further be assumed that the difference between the S-033188 and placebo groups is 54 hours (96 hours in the S-033188 group, 150 hours in the placebo group). In the past, placebo-controlled clinical trials of oseltamivir for the otherwise healthy and high risk patients, have demonstrated that the difference in the median time to alleviation of symptoms between the placebo group and the oseltamivir group for the otherwise healthy patients was larger than that in the studies of high risk patients. Therefore, it is speculated that the difference between the S-033188 group will be < 54 hours.

The required sample size will therefore be calculated based on the conservative assumption of a 36-hour difference (assuming that the median time to improvement of influenza symptoms in the placebo group and the S-033188 group was 150 and 114 hours, respectively) in the median time to improvement of influenza symptoms between the S-033188 group and the placebo group to ensure at least 90% power in the efficacy evaluation of S-033188.

Patients will be randomized on a 1:1 basis to either S-033188 or placebo and a follow-up period will be 336 hours (14 days). Assuming that the time follows an exponential distribution, the study will require 790 patients in the ITTI population in order for the generalized Wilcoxon test to have 90% or more power with a 2-sided significance level of 5% (395 patients in the S-033188 group and placebo group, respectively).

Using a 1:1 randomization ratio between the S-033188 group and the oseltamivir group, the ITTI population of oseltamivir will be 395 patients. Table 9-1 shows the statistical power to compare between the S-033188 group and the oseltamivir group under several sets of assumed time to improvement of influenza symptoms.

Table 9-1	Statistical Power to Compare Between S-033188 and
	Oseltamivir

Median Time to Alleviation of Symptoms (S-033188, Oseltamivir)	Statistical Power for Comparison Between S-033188 and Oseltamivir by Generalized Wilcoxon Test
(114 hours, 126 hours)	22.3%
(108 hours, 126 hours)	45.3%
(102 hours, 126 hours)	71.5%
(96 hours, 126 hours)	90.2%

9.4 Handling of Missing Data

Missing data will not be replaced for the primary analyses. A sensitivity analysis will follow a predefined rule for missing data.

9.5 Patient Disposition

Among the patients randomized to each treatment group, the number and percent of patients who complete the study and the number and percent of patients who prematurely discontinue from the study will be summarized by treatment group. In addition, reasons leading to study discontinuation will be summarized for each treatment group.

The number and percent of patients for the randomized patients included in the ITTI, safety, and PPS populations will also be presented.

9.6 Demographic and Baseline Characteristics

Demographic and baseline characteristics for the ITTI population will be summarized with descriptive statistics by treatment group.

9.7 Extent of Exposure and Treatment Compliance

For the ITTI and safety populations, whether each patient receives the study drug or not will be presented in a listing. The number of days when the study drug is taken and the percent compliance will be summarized with descriptive statistics by the treatment group for the safety population.

9.8 **Prior Therapies**

Prior therapies for drugs will be coded using the World Health Organization (WHO) Drug Dictionary. In the ITTI population and the Safety population, the number of patients using each prior drug will be counted by treatment group. The number of patients using each prior therapy will also be counted. Patients who received prior therapy will be listed for the safety population.

9.9 Concomitant Therapies

Concomitant therapies for drugs will be coded using the WHO Drug Dictionary. In the ITTI population and the Safety population, the number of patients using each concomitant drug will be summarized by treatment group. The number of patients using each concomitant therapy will also be counted. Patients who received concomitant therapies will be listed for the safety population.

9.10 Efficacy Analyses

The ITTI will be the primary population for efficacy analyses. The PPS will be used for sensitivity analyses.

9.10.1 Primary Efficacy Endpoint Analyses

The primary efficacy endpoint will be the time to improvement of influenza symptoms (with modification for preexisting symptoms):

- Preexisting symptoms (ie, cough, fatigue, or muscle/joint pain that existed prior to developing influenza) that were judged by the patient to be worse at baseline (ie, the predose examinations) must improve from baseline severity
 - o Improvement in baseline severity is as follows:
 - Severe \rightarrow moderate, mild, or absent
 - Moderate \rightarrow mild or absent
 - Note: At baseline (ie, the predose examinations), patients will only be asked if
 preexisting symptoms existed (within the last 30 days) and if they were
 worsened by influenza. Patients will be asked to rate the severity at baseline
 that is the severity that needs to improve. To avoid recall bias, patients will
 not be asked to rate the severity of preexisting symptoms prior to influenza.
- Preexisting symptoms (ie, cough, fatigue, or muscle/joint pain that existed prior to developing influenza) that were judged by the patient to NOT be worse at baseline (ie, the predose examinations) must have their baseline severity maintained

- o Maintenance of baseline severity is as follows:
 - Severe \rightarrow Severe
 - Moderate \rightarrow Moderate
- For new symptoms at baseline (ie, the predose examinations), alleviation of symptoms assessment will not be modified
 - Alleviation of symptoms is as follows:
 - Severe \rightarrow mild or absent
 - Moderate \rightarrow mild or absent

Once all of a patient's influenza symptoms are alleviated, maintained, or improved as defined above, the endpoint for that patient will be reached, for a duration of at least 21.5 hours (24 hours – 10%).

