7.4.1.2 Assessment of Severity of Influenza Symptoms

The patient will self-assess 7 symptoms associated with influenza (cough, sore throat, headache, nasal congestion, feverishness or chills, muscle or joint pain, and fatigue) on a 4-point rating scale (0, None; 1, Mild; 2, Moderate; 3, Severe).

The patient will assess and record on a paper questionnaire, influenza symptoms predose on Day 1; then subsequent influenza symptoms will be assessed and recorded in the patient eDiary twice daily (morning and evening) until Day 9, and once daily (evening) from Days 10 to 14. Table 7-2 provides the time windows of assessment as a guide.

18:00 -

of Severity of Influenza Symptoms		
Assessment Period	Time Period of a Day	Time Window as a Guide
Days 1 to 9	Morning	- 11:59
	Evening	18:00 -

Evening

Table 7-2 Time Windows of Assessment as a Guide: Assessment

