9.10.2 Secondary Efficacy Endpoints

The secondary efficacy endpoints include the following variables.

1) Proportion of patients positive for virus titer and proportion of patients positive by RT-PCR at each time point

Defined as the percentage of patients whose virus titer is not < the lower limit of quantification among those assessed for virus titer, and the percentage of patients with detectable virus RNA among assessed by RT-PCR, respectively.

2) Change from baseline in virus titer and in the amount of virus (RT-PCR) at each time point

Defined as the change from baseline in virus titer and the change from baseline in the amount of virus RNA, respectively. Baseline is defined as the last value obtained before the initial dose.

3) AUC adjusted by baseline in virus titer and in the amount of virus RNA (RT-PCR)

Defined as AUC, where AUC is the area under the curve, of change from baseline in virus titer and AUC of change from baseline in the amount of virus RNA, respectively. AUC is calculated using the trapezoidal method.

4) Time to cessation of viral shedding by virus titer and by RT-PCR

Defined as the time between the initiation of the study treatment and first time when the virus titer is < the lower limit of quantification and the time between the initiation of the study treatment and first time when virus RNA by RT-PCR is < the lower limit of quantification, respectively.

5) Proportion of patients whose symptoms has been alleviated at each time point

Defined as the percentage of patients whose primary endpoints are improved after the initiation of the study treatment in the analysis population by each time point. 6) Time to alleviation of symptoms (cough, sore throat, headache, nasal congestion, feverishness or chills, muscle or joint pain, and fatigue)

Defined as the time between the initiation of the study treatment and the alleviation of influenza symptoms. The alleviation of influenza symptoms is defined as the time when all of 7 influenza symptoms have been assessed by the patient as 0 (None) or 1 (Mild) in the patient eDiary, for a duration of at least 21.5 hours (24 hours -10%).

7) Time to improvement in the 4 systemic symptoms (headache, feverishness or chills, muscle/joint pain, and fatigue)

Defined as the time between the initiation of the study treatment and the improvement in the 4 systemic symptoms. The assessment follows the criteria for the primary endpoint.

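### The primary endpoint's rule for chronic symptoms that influenza did not worsen accepts only an unchanged score, so on its literal wording a symptom that gets better fails the rule

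*Protocol*

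**What the plan says.** Protocol 9.10.1 sorts the symptoms present at baseline into three categories and gives each its own rule.

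- **Preexisting and worse at baseline:** must improve. The list accepts severe going to moderate, mild or absent, and moderate going to mild or absent.
- **Preexisting and not worse at baseline:** "must have their baseline severity maintained". The list has two entries: Severe to Severe, and Moderate to Moderate.
- **New:** must be alleviated. The list accepts severe or moderate going to mild or absent.

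The section closes: "Once all of a patient's influenza symptoms are alleviated, maintained, or improved as defined above, the endpoint for that patient will be reached", with a required duration of at least 21.5 hours.

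Protocol 7.9.1 gives the reason for the modification. It is meant to permit improvement of a worsened chronic symptom, "or maintenance of a preexisting symptom that has not been worsened by the onset of acute influenza", so as to "avoid confounding of results due to persistent preexisting symptoms that cannot be completely alleviated".

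Symptoms are scored on a "4-point rating scale (0, None; 1, Mild; 2, Moderate; 3, Severe"), according to Protocol 7.4.1.2.

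In Protocol 9.10.2, endpoint 6 (time to alleviation) requires that "all of 7 influenza symptoms have been assessed by the patient as 0 (None) or 1 (Mild) in the patient eDiary". Endpoint 5 is defined as "the percentage of patients whose primary endpoints are improved after the initiation of the study treatment". Endpoints 7 and 8 each state: "The assessment follows the criteria for the primary endpoint".

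**The concern.** The middle list has no entry for a score below baseline and no words such as *or better*. Followed bullet by bullet, a chronic symptom that falls below its baseline score does not satisfy the rule for its own category, and the patient has no event at that time. That penalises recovery, which is the opposite of what 7.9.1 sets out to do.

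The event definition of the primary analysis is at stake. Two programmers could follow 9.10.1 faithfully and derive different event times for the same diary. The category is one the Protocol foresees: asthma or chronic lung disease qualifies a patient for entry (4.2, item 6a), 7.9.1 uses cough in chronic lung disease as its example, and 9.10.3.2 (item 12) has an explicit exclusion for moderate or severe symptoms that are preexisting and not worsened.

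**Working it through.** **The plan's own figure.** The sample size rests on this endpoint, so I reproduced it first. Inputs from Protocol 9.1 and 9.2: medians of 114 and 150 hours, exponential times, 336 hours of follow-up, 1:1 allocation, generalized Wilcoxon test, two-sided 5%. With hazards λ = ln 2 / median, survival S = exp(−λt), weight w = (S₁ + S₂)/2, at-risk share p = S₁/(S₁ + S₂), hazard ratio θ = λ₁/λ₂ and D the expected events in each time interval:

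- E = Σ D·w·[pθ/(pθ + 1 − p) − p]
- V = Σ D·w²·p(1 − p)
- power = Φ(|E|/√V − 1.96)

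This gives 90.0% at 395 per arm, and 395 is the smallest number that reaches 90%. Table 9-1 also reproduces: 22.2, 45.3, 71.5 and 90.2%, against the stated 22.3, 45.3, 71.5 and 90.2%. These figures are not in dispute.

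**Enumeration.** Take one symptom with a baseline score of 2 or 3, the only baseline scores that the lists in 9.10.1 cover. It can later be scored 0, 1, 2 or 3, so there are 2 × 4 = 8 pairs. Check each pair against four rules: the maintenance list alone; the union of the three lists in 9.10.1 (the looser reading of the closing sentence); the 0-or-1 rule of endpoint 6; and no worse than baseline.

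| Baseline → later | Maintenance list | Union of three lists | Endpoint 6 | No worse than baseline |
|---|---|---|---|---|
| 2 → 0 | no | yes | yes | yes |
| 2 → 1 | no | yes | yes | yes |
| 2 → 2 | yes | yes | no | yes |
| 2 → 3 | no | no | no | no |
| 3 → 0 | no | yes | yes | yes |
| 3 → 1 | no | yes | yes | yes |
| 3 → 2 | no | yes | no | yes |
| 3 → 3 | yes | yes | no | yes |
| **Accepted** | **2** | **7** | **4** | **7** |

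What follows:

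1. The two readings of 9.10.1 differ in 7 − 2 = 5 of the 8 pairs. These five are exactly the better-than-baseline outcomes.
2. Four of those five meet endpoint 6.
3. The maintenance list and endpoint 6 share no pair. For such a symptom, no score satisfies both rules at the same diary entry. A patient with all seven symptoms at 0 would be alleviated under endpoint 6 and not improved under the primary endpoint.
4. No worse than baseline shares all 4 of endpoint 6's pairs, so that conflict disappears. Only 2 → 3, a true worsening, still fails.

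**Illustration only.** The Protocol does not say how many patients the literal rule would block. Assume that a share f of each arm never meets it within 336 hours, so that S = f + (1 − f)·exp(−λt). Power at 395 per arm is then:

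| Assumed f | Power |
|---|---|
| 0% | 90.0% |
| 2% | 88.4% |
| 5% | 85.7% |
| 10% | 80.6% |
| 20% | 68.3% |

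These values of f are assumptions, and the same f is applied to both arms. The table shows how power would respond. It is not an estimate of loss in this trial.

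**The case against.** The best counter-argument is that the bullet-by-bullet reading cannot have been meant.

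- **The lists are not complete tables.** None covers a baseline of none or mild, although inclusion criterion 3b requires only one general and one respiratory symptom at moderate or worse, so five of the seven may enter at 0 or 1. If only listed transitions counted, such patients could never have an event.
- **Section 7.9.1 is permissive.** It presents the endpoint as a relaxation of time to alleviation. A relaxation would not withdraw mild or absent as an acceptable outcome, which covers 4 of the 5 disputed pairs. The fifth, severe to moderate, follows all the more where severe to severe is accepted.
- **Item 12 in 9.10.3.2** excludes moderate or severe symptoms that are preexisting and not worsened, alongside none and mild, as if both were already at target.
- **The closing sentence of 9.10.1** can be read as letting any of the three states count.
- **The affected group is narrow and uncounted,** and the SAP, which I have not seen, may settle the derivation.

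The first four points are good evidence of intent: *or better* was almost certainly meant. They do not supply the missing words. The closing sentence refers back to the definitions above it. If it let any state count for any symptom, a new severe symptom that stayed severe would count as maintained, against the rule for new symptoms. It therefore has to be read category by category, which leads back to the narrow list.

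On size, the objection stands: the Protocol does not show that the group is large. On the SAP, 9.1 says it is to follow the Protocol's statistical section and to give reasons for departures. Programming no worse than baseline would arguably depart from the listed rule, so the Protocol is the place to correct it.

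**Conclusion.** The point holds. As written, the maintenance rule in 9.10.1 accepts 2 of 8 score pairs and leaves out all 5 improvements, while a looser reading accepts 7. The primary event, and secondary endpoints 5, 7 and 8, depend on which reading is programmed.

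The point is limited to cough, fatigue or muscle/joint pain that is preexisting, moderate or severe at baseline, judged not worse with influenza, and later scored below baseline. A worsened preexisting symptom that falls below baseline meets its own rule.

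This is a defect of wording in the primary endpoint, not a wrong figure. The 395 per arm and Table 9-1 stand. The number of affected patients, and any effect on power, cannot be determined from the Protocol. It should be fixed, because the event definition of the primary analysis should have one reading.

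**What to change.** In 9.10.1, define maintenance as no worse than baseline severity and complete the list: *Severe to severe, moderate, mild or absent; Moderate to moderate, mild or absent*. Carry the same rule into the derivation of the primary endpoint and of secondary endpoints 5, 7 and 8, and settle it before unblinding.

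The cost is a few words and the matching programming. It needs no new data, no extra patients and no change to the sample size.

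A separate editorial note: item 12 of 9.10.2 is titled as improvement but applies the 0-or-1 alleviation rule. It differs from the primary rule in one case, severe to moderate in a preexisting, worsened symptom. Retitling it as time to alleviation of each symptom would remove the mismatch; applying the primary rule there would do so too.
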